Effects of a high-intensity interval training (HIIT) exercise intervention on sleep quality in
women exposed to trauma: A randomized controlled trial

Date: 9/16/2021

Methods

C.2 Research design. A randomized control trial design will be used. Participants will be randomly assigned to one of the two treatment arms in blocks of two to optimize statistical power and minimize potential bias (Spieth et al., 2016). Sequentially numbered sealed envelopes created by a third-party using research randomizer (www.randomizer.org) will be used to allocate participants to treatments.

C.3 Participants. Seventy-two women who meet the inclusion criteria will be invited to participate. The seven inclusion criteria are: (i) exposure to a traumatic event, (ii) persistent PTSD-related symptoms adequate to screen positive for PTSD (Posttraumatic Diagnostic Scale-5 total scores > 27), (iii) poor sleep quality (Pittsburgh Sleep Quality Index >5), (iv) failure to meet recommended level of physical activity for U.S. adults (<150-mins of moderate or 75-mins of vigorous physical activity [or a combination] per week), (v) able to safely perform high intensity exercise (no contraindications based on the Physical Activity Readiness Questionnaire), (vi) aged 18-39 years, (vii) a non-smoker, (viii) willing to avoid alcohol and vigorous physical activity 24 hours before visiting the lab, and (ix) willing to avoid caffeine for 12 hours before visiting the lab.

C.4 Recruitment.

Several recruitment approaches will be implemented to ensure the required sample size is obtained. These approaches included: (i) e-mails sent to selected campus listservs, (ii) recruitment announcements in college classrooms, (iii) flyers placed in the University Health Center and around town, (iv) public service announcement made over the radio, and (v) by word of mouth.

C.5 Online Screening. Individuals interested in volunteering will be screened for eligibility by completing online surveys presented using Qualtrics. Eligible individuals will be invited to visit the Exercise Psychology Laboratory.

C.6 Baseline and Post-intervention. Prior to the testing, individuals will be asked to avoid alcohol consumption and moderate to vigorous physical activity 24 hours prior. Following the informed consent process, individuals will complete a brief menstrual history, 24-hour health status recall, and provide a saliva sample. Information about potential confounders and psychological symptoms also will be obtained using standardized methods supported by evidence of their validity (i.e., measures of symptoms of depression and anxiety, anxiety sensitivity, and physical activity history). These assessments will be repeated every 2 weeks and at the end of the six-week experiment. A body composition assessment via a dual-energy x-ray absorptiometry (DXA) will be completed. In a private room, the participants will fasten a wireless Zephyr™ BioHarness™ (Zephyr Technology, Auckland, New Zealand) below the sternum, (see figure 3). The Zephyr™ BioHarness™ will assess autonomic function via variability in heart rate. A baseline heart rate variability will involve adopting a seated position and measuring ECG while the participants rest for 5 minutes. Participants will complete the state portion of the State-Trait Anxiety Inventory (STAI), followed by a mental arithmetic task in which the participant will subtract by 13 from a 4-digit number for 10 minutes. Immediately after the mental arithmetic, participants will complete the state portion of the STAI. Participants will then complete a seated recovery for 5 minutes. Next, peak oxygen uptake (VO_{2Peak}) and peak power output (PPO) will be measured via a ramped bicycle protocol (Lode Excalibur Sport). Power output will be increased by 15 watts every minute until volitional exhaustion. Expired gases will be continuously measured via indirect calorimetry (Parvo Medics TrueOne 2400;

Parvo Medics, Salt Lake City, UT), and heart rate will be continuously monitored throughout the exercise test via a chest heart monitor (Polar; Polar Electro Inc., Lake Success, NY). The VO_{2peak} test will be administered so that participants can be prescribed the same exercise intensity, relative to their PPO, during exercise training. Saliva, DXA, vagal tone, peak oxygen uptake (VO_{2peak}), and sleep will be measured at baseline and after the six-week intervention.

C. 7 High-Intensity Interval Training (HIIT). HIIT participants will complete three leg cycle ergometer bouts weekly. During the first two weeks, the participants will complete 13, 30-second high intensity exercise intervals at a wattage prescribed to elicit 67% of PPO. Each 30-second exercise interval will be followed by a 1-minute active recovery interval at 30% of PPO. Each week, prescribed wattage will be increased by 4% of PPO. Thus, in the final week, the training intensity will be at 87% of PPO (See table 1 for training example). At the start of the third week, the exercise duration will be increased. Specifically, the 13, 30-second-high intensity intervals will increase to 10, 60-second high intensity intervals. All sessions will start with a three-minute warm-up and end with a two-minute cool-down on the cycle ergometer. In sedentary panic disorder patients, a 12 day HIIT training intervention of similar initial exercise intensity was well tolerated and showed rapid reductions in symptoms (Plag, Ergec, Fydrich, & Strohle, 2019). During the exercise sessions, ratings of perceived exertion, quadriceps pain, and heart rate during the exercise sessions will be assessed 0, 5, 10, 15, 20 minutes into the HIIT.

C.7 Waitlist Control (WL). Participants randomly assigned to the waitlist will visit the laboratory in order to complete the baseline, bi-monthly assessments and post-assessments. They will be asked to maintain their current lifestyle. They will be given the option to receive a six-week supervised HIIT training program after the waitlist participation.

D. Primary Outcome Measures for the Specific Aim

D.1 Specific Aim 1. Evaluate the impact of six-weeks of high intensity interval training on sleep quality and whether the effect is accounted for by the change in vagal tone.

Pittsburgh Sleep Quality Index-(PSQI): The PSQI is the gold standard measure of self-reported sleep quality. It consists of 19 items. Scores range from 0-21, higher scores indicate poorer sleep quality. A global score ≥ 5 indicates poor sleep quality with a sensitivity of 0.90 and specificity of 0.87 compared to polysomnographically determined poor sleep (Buysse et al., 1989). The PSQI instructions will be modified to better assess rapid changes in usual sleep habits (last two weeks rather than the past month).

Cardiac Vagal Tone: Each participant will place a bioharness monitor on in a private room. The R-R waveform will be sampled at 1000 hertz. Fast Fourier transformation will be applied, spectral power will be determined, and the average of the frequency domain will be calculated using Kubios analysis software (Tarvainen, Niskanen, Lipponen, Ranta-aho, & Karjalainen, 2014). After the frequency units from the heart cycles are converted to hertz, the vagal tone (high frequency band; 0.15-0.5 Hz), sympathetic tone (low frequency band; 0.05-0.15 Hz) and total power (0.017-0.5 Hz) will be calculated. The *apriori* focus is on changes in vagal tone.

Arithmetic Stress Task: Vagal tone will be measured at rest and during a stressor involving math calculations. Serial subtraction will be administered by a research team member dressed in white lab coat, with a clip board and pen for making notes. The team member will correct participants every time an incorrect answer is given and prompt participants to increase their pace every 15 seconds. Serial subtraction will involve sequentially subtracting 13 from a 4-digit number, and if an incorrect response is given, they will be asked to start over. The subtraction task will last a total of 10 minutes.

D.1.1 Expected Results. Based on our review of exercise training studies (McGranahan & O'Connor, 2021), we hypothesize HIIT to result in a clinically meaningful, moderate-sized or greater improvement in sleep quality. It is hypothesized that exercise-training induced changes in vagal tone will mediate the improvements in sleep quality. We do not expect improvements for sleep quality or vagal tone in the control group.

D.1.2 Statistical Power. A sample of 60 total participants will provide statistical power of 80%, at an alpha of 0.05. Assuming a moderate-sized interaction effect of 0.47 on sleep quality and a correlation of 0.85 between repeated measurements, the calculated sample size is 30 per group. Meta-analyses of participant drop out in exercise training trials shows that an average of 20% in the exercise groups and 15% in the control groups drop out (Kelley & Kelley, 2013). Using 20% attrition, recruiting 36 per group will result in 30 completers per group. The short-term (six-week) training duration should result in less than 20% compared to the meta-analysis which included primarily longer-term trials.

D.1.3 Statistical Analysis. ANOVA will examine the effect of exercise training on sleep quality. Mediation of the effect by the change in vagal tone will be tested by adding the variable as a covariate to the model. A change in the significance of the f-value would indicate significant mediation (Baron & Kenny, 1986; Fiske, Kenny, & Taylor, 1982). To quantify the effect size exercise training has on sleep quality at weeks 2, 4, and 6 and vagal tone at baseline and post, Hedges' d will be calculated.

D. 2.0 Specific Aim 2. Evaluate the impact of six-weeks of high intensity interval training on sleep quality, statistically testing for the effect of the change in trait anxiety and hyperarousal symptoms.

State and Trait Anxiety Inventory: Trait anxiety will be used and is reduced after exercise training (J. W. Whitworth et al., 2019a).

The Posttraumatic Diagnostic Scale-5 (PDS-5): Hyperarousal symptoms will be measured using the hyperarousal subscale of the Posttraumatic Diagnostic Scale-5 (PDS-5). The full 24-item scale also will be used as part of the inclusion criteria to assess PTSD symptoms in the past month based on the diagnostic criteria for the DMS-5. The full PDS-5 assesses trauma history, symptom onset, and index of trauma. Internal consistency of the full PDS-5 and the hyperarousal subscale ≥ 0.90 .

D.2.1 Expected Results. Hyperarousal and anxiety symptoms are expected to decrease after HIIT and be correlated with improvements in sleep quality.

D.2.2 Statistical Analysis. A time-varying covariate analysis will determine if sleep quality changes are explained by the change in trait anxiety or hyperarousal at weeks 2-, 4-, or 6- of the intervention (Winer, 1991). To quantify the effect size exercise training has on PTSD symptoms and anxiety at weeks 2, 4, and 6, Hedges' d will be calculated.

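### Fixed blocks of two let every second allocation be deduced from the one before, and the plan does not say that the block size is withheld or staff masked

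*Combined protocol and SAP*

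**What the plan says.** The allocation plan is confined to section C.2. It reads: "Participants will be randomly assigned to one of the two treatment arms in blocks of two to optimize statistical power and minimize potential bias". It then names the concealment device: "Sequentially numbered sealed envelopes created by a third-party using research randomizer". Section D.1.2 shows that the ratio is 1:1: "recruiting 36 per group will result in 30 completers per group". Each block of two therefore holds one HIIT place and one waitlist place, and 72 women make 36 blocks.

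Other sections bear on what staff can see and do:

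- **Invitation (C.5).** After online screening, "Eligible individuals will be invited to visit the Exercise Psychology Laboratory".
- **Consent and baseline (C.6).** "Following the informed consent process, individuals will complete a brief menstrual history", and laboratory tests come next.
- **Training (C.7, HIIT).** Women cycle three times a week under observation; for example, "heart rate during the exercise sessions will be assessed 0, 5, 10, 15, 20 minutes into the HIIT". The waitlist arm keeps its usual lifestyle, and there is no sham.
- **Arithmetic stress task (section D).** "The team member will correct participants every time an incorrect answer is given and prompt participants to increase their pace every 15 seconds".

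The document does not say that the block size is withheld from staff, that anyone is masked, that those who enrol are separate from those who train, or who opens each envelope and when. The waitlist paragraph of C.7 describes women already assigned to the waitlist as attending for baseline, which can be read as allocation before baseline testing.

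**The concern.** Concealment is meant to keep the person enrolling a participant from knowing which arm comes next. Numbered, sealed envelopes made by a third party protect the first place in each pair. They do not protect the second, which is simply the opposite of the first. The block size is printed in the protocol, and the previous woman's arm shows in whether she comes in to train.

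Screening online against mostly fixed cut-offs leaves little discretion over eligibility. What can still be influenced is whom the laboratory invites and when, how the consent discussion goes, and how staff-led baseline tests are run. If the next arm is known, encouragement, timing or test conduct may differ by expected arm, knowingly or not. Resulting differences in measured baseline sleep, symptoms or activity could be seen and partly adjusted for. Differences in unmeasured features, such as motivation to change sleep or lifestyle, could not. This matters more because the primary outcome, the PSQI, is self-reported.

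**Working it through.** The plan gives no figure for predictability, so there is none to reproduce.

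**Inputs from the document.** Block size 2 (C.2); 72 women (C.3); 36 per arm (D.1.2); cited dropout of 20% in exercise arms and 15% in control arms (D.1.2).

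**Assumed observer.** Someone who knows the block scheme and all past allocations, and who always guesses the arm with more places left. Ties count as one half.

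**Step 1. Fixed blocks.** In a block of 2m, the expected share of allocations that are certain is 1/(m + 1), because one arm's places run out before the block ends.

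- Block of 2: certain 1/2; correct (0.5 + 1)/2 = 0.75.
- Block of 4: certain 1/3; correct (0.5 + 2/3 + 2/3 + 1)/4 = 0.708.
- Block of 6: certain 1/4; correct 0.683, by listing all sequences.

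**Step 2. Random mix of 4 and 6.** Sizes were equally likely, over 20,000 simulated lists of 72. The observer knew the set of sizes but not their order.

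| Scheme | Certain | Guessed correctly | Of 72: certain / correct |
|---|---|---|---|
| Blocks of 2 (plan) | 50% | 75% | 36 / 54 |
| Fixed 4 | 33% | 71% | 24 / 51 |
| Fixed 6 | 25% | 68% | 18 / 49 |
| Mix of 4 and 6 | 5.6% | 69% | about 4 / about 50 |
| No foreknowledge | 0% | 50% | 0 / 36 |

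**Step 3. What steering could do (an illustration on an assumption outside the document).** Suppose women entered when HIIT is predicted differ in outcome by +e SD, and those entered when waitlist is predicted by −e SD. The expected false difference between arms is:

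- acting only on certainties: 2 × share certain × e;
- acting on every best guess: 4 × (share correct − 0.5) × e.

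For blocks of two: 2 × 0.50 × e = 1.0e, and 4 × 0.25 × e = 1.0e. For the mix: 2 × 0.056 × e = 0.11e, and 4 × 0.191 × e = 0.76e. With e from 0.1 to 0.3 SD, blocks of two give 0.10 to 0.30 SD. The mix gives 0.01 to 0.03 SD on certainties, or 0.08 to 0.23 SD on best guesses.

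**Step 4. What exact balance buys.** At exactly 72, the mix ends 35 v 37 in about 23% of lists and 36 v 36 otherwise. If enrolment stops at an odd number, the difference can reach 3. For a two-sample t test at alpha 0.05, with the effect set so that 30 v 30 gives 80.0% power, 29 v 31 gives 79.96% and a difference of 3 (28.5 v 31.5) gives 79.90%.

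D.1.2 cites dropout such that "an average of 20% in the exercise groups and 15% in the control groups drop out". Those rates alone would leave 36 × 0.80 = 28.8 and 36 × 0.85 = 30.6 completers, so exact balance at entry would not survive to the analysis.

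**The case against.** The arithmetic is not in dispute. The case against concerns how much it matters.

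- **Opportunity and motive are narrow.** A third party makes the list, women volunteer through broad advertising, screening is online, and waitlisted women are later offered HIIT. This stands, and it is why the point is a risk and not a finding of bias.
- **The gap may be one of reporting.** The document does not say who enrols, trains or opens envelopes; in practice these may be separate people. That is possible, but the block rule is stated, and followed as written it makes half the allocations deducible.
- **Some steering would largely wash out.** If it created only a stable difference in PSQI, a group-by-time contrast would cancel it. Adjustment for baseline with the plan's correlation of 0.85 would leave about (1 − 0.85)e = 0.15e, or 0.015 to 0.045 SD. This stands. The full range in Step 3 applies only to features that affect change in sleep, and the conclusion does not rest on it.
- **The arithmetic task has no evident direct route to PSQI.** True. It feeds vagal tone, the proposed mediator, and state anxiety.
- **Mixed blocks barely reduce guessing.** The fall is from 75% to 69%. This also stands: the remedy removes most of the certainty, not the ability to guess.
- **Small blocks also balance the arms over calendar time.** They do, and blocks of 4 and 6 keep most of that benefit.

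**Conclusion.** The concern holds. Under C.2 as written, 36 of 72 allocations can be deduced with certainty by anyone who knows the block size and the preceding assignment, and the best guess is right for 54 of 72. The document rules out neither piece of knowledge: it prints the block size, and the arms are openly different. The choice works against the plan's stated aim of limiting bias, and its contribution to power is about 0.1 percentage point or less.

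The conclusion assumes 1:1 blocks used as described and an enroller with access to both facts. It does not assume that anyone has steered or would steer allocation, and any SD figure for bias rests on an assumed e. The change should be made because it is cheap; nothing here shows that the trial's result would be wrong.

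**What to change.** In C.2, replace the fixed block of two with randomly permuted blocks of varying size (for example 4 and 6), generated by the same third party. Suggested text:

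> Allocation will use randomly permuted blocks of varying size, prepared by a third party who withholds the block sizes from anyone who recruits, screens or tests participants. Each envelope will be opened only after eligibility, consent and baseline testing are complete.

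The actual sizes are best kept in the third party's own record and not printed in the protocol. The 5.6% and 69% above already assume that the set of sizes is known, so withholding it can only help.

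The cost is one new list and two sentences. The downside is a possible final imbalance of 2 women at 72, or 3 if enrolment stops at an odd number. No arm, outcome, visit or sample size changes. The fix does not mask staff once women are assigned, so test conduct after the intervention could still differ by arm.

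### The screening PSQI has no role in the analysis; prespecifying it beside the baseline PSQI in a week-6 ANCOVA costs almost nothing and could cut residual variance by 0% to about 21%

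*Combined protocol and SAP*

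**What the plan says.** - **Entry gate (C.3).** One inclusion criterion is "poor sleep quality (Pittsburgh Sleep Quality Index >5", so eligibility cannot be decided without a PSQI score.
- **When the gate is applied (C.5).** "Individuals interested in volunteering will be screened for eligibility by completing online surveys presented using Qualtrics". The next step is "Eligible individuals will be invited to visit the Exercise Psychology Laboratory". The score used for entry therefore comes before the laboratory visit.
- **Second measurement (C.6).** The list of visit measures ends "and sleep will be measured at baseline and after the six-week intervention". The PSQI is not named there. It is described under Specific Aim 1 (D.1) as the sleep-quality measure, with its recall period shortened from a month to two weeks.
- **Order of baseline and allocation.** This is not stated. The waitlist paragraph (the second section numbered C.7) reads "Participants randomly assigned to the waitlist will visit the laboratory in order to complete the baseline, bi-monthly assessments and post-assessments", which can be taken to mean that allocation comes first.
- **Analysis (D.1.3).** "ANOVA will examine the effect of exercise training on sleep quality". The only covariates named in D.1.3 and D.2.2 are changes in vagal tone, trait anxiety and hyperarousal. No pre-treatment PSQI is named.
- **Power (D.1.2).** 30 completers per group, 80% power, alpha 0.05, an interaction effect of 0.47, and a correlation of 0.85 between repeated measurements.

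**The concern.** A single PSQI score carries occasion-to-occasion error. Two pre-treatment scores together usually describe a woman's usual sleep better than one, and a better pre-treatment predictor makes the comparison between arms more precise. The screening score must be collected for the trial to run, yet the plan describes no use for it beyond entry. With 60 completers planned, precision on the primary outcome is worth having when the data are already in hand.

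The screening score also has a property that the baseline score may lack. It determines eligibility, so it precedes assignment. If the baseline visit takes place after allocation is known, the screening PSQI is the only clearly pre-randomisation measure of the primary outcome.

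What is at stake is the width of the interval and, if 0.85 is optimistic, power. Validity is not at stake.

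**Working it through.** **Inputs.** From D.1.2: effect 0.47 (taken as SD units), correlation 0.85, 30 per group, alpha 0.05 (taken as two-sided). The documents give no correlation for the screening score, so every such value below is an assumption.

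**The plan's own figure.** Standard two-group formulas with the noncentral t do not reproduce 30 per group for 80% power.
- Change from baseline: variance 2(1 − 0.85) = 0.300, giving 23 per group. Power at 30 is 90.5%.
- ANCOVA on one baseline score: variance 1 − 0.85² = 0.2775, giving 21 per group. Power at 30 is 92.5%.
- Group-by-time F test over four times with a linearly growing effect (a pattern the plan does not state): 28 per group, the nearest two-group result.

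On the stated inputs, the one-baseline analyses therefore start above 90% power.

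**Formulas.** Let r1 be the baseline–week 6 correlation, r2 screening–week 6, and r12 screening–baseline.
- One covariate: V1 = 1 − r1².
- Two covariates: V2 = 1 − (r1² + r2² − 2·r1·r2·r12)/(1 − r12²).
- Power: noncentral t with standard error √(2V/30) and 58 degrees of freedom less one per covariate.

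Worked case, all 0.85: with a common r, V2 = 1 − 2r²/(1 + r) = 1 − 1.445/1.85 = 0.2189. The cut is 1 − 0.2189/0.2775 = 21%, equivalent to 0.2775/0.2189 = 1.27, or about 27% more women.

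| r1, r2, r12 | V1 | V2 | Cut | Power at 30 per arm |
|---|---|---|---|---|
| 0.85, 0.85, 0.85 | 0.2775 | 0.2189 | 21% | 92.5% to 96.9% |
| 0.85, 0.75, 0.75 | 0.2775 | 0.2486 | 10% | 92.5% to 94.8% |
| 0.85, 0.70, 0.70 | 0.2775 | 0.2559 | 8% | 92.5% to 94.3% |
| 0.85, 0.75, 0.85 | 0.2775 | 0.2748 | 1% | 92.5% to 92.7% |
| 0.85, 0.7225, 0.85 | 0.2775 | 0.2775 | 0% | 92.46% to 92.45% |
| 0.70, 0.70, 0.70 | 0.5100 | 0.4235 | 17% | 71% to 78% |
| 0.60, 0.60, 0.60 | 0.6400 | 0.5500 | 14% | 61% to 67% |

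The 0% row is a first-order autoregressive pattern (0.85 × 0.85 = 0.7225): once baseline is known, screening adds nothing.

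**Interval width.** With all correlations 0.85, the 95% half-width falls from 0.272 to 0.242 SD, and 1 − 0.242/0.272 = 11%.

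**Range restriction.** The entry gate truncates the screening score. Trivariate normal data with all correlations 0.85 before selection were simulated. If the gate removes the lowest 30%, 50% or 70% of women (assumed), the cut is 17%, 15% or 13%.

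**The case against.** **Two pre-randomisation scores are not a stated fact.** A reader might infer that every randomised woman is known to have two PSQI scores before randomisation. The documents do not support that. C.6 names no sleep instrument, the screening score could be carried forward as baseline, and the order of baseline and allocation is open. This stands, and it limits the point to one screening score that should exist and a second that is likely.

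**The gain is not guaranteed.** A reader might also infer that a second pre-treatment score helps whatever the correlation. That is true for a common correlation below 1, but under time-decaying correlation the gain is zero. This stands.

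**The gain depends on the model.** If all correlations are equal, the screening score is uncorrelated with change from baseline (0.85 − 0.85 = 0). As an added covariate in a change-score or group-by-time ANOVA it would remove no error. This stands: the gain calculated here requires the week-6 ANCOVA, which D.1.3 does not specify. Whether the ANOVA adjusts for baseline at all has to be settled first.

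**It does not rescue an underpowered test.** On the plan's own inputs, a one-baseline ANCOVA has about 92% power. This stands.

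**The cost may exceed one sentence.** C.6 places informed consent at the visit, after online screening. The consent pages are not available here, so it cannot be seen whether research use of screening responses is covered. Nor is it stated whether the two-week recall applies at screening. Both are conditions on the fix.

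**Using an entry score only for entry is ordinary practice.** That is fair: nothing here is contradictory or invalid. It does not answer the fix, because if the score adds nothing the power loss is only 92.46% to 92.45%.

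**Conclusion.** The point holds as a nearly free improvement and does not identify an error. A screening PSQI should exist for every enrolled woman, and the plan gives neither it nor the baseline score a role as covariate in the primary analysis.

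Relative to a one-baseline ANCOVA, the screening score reduces residual variance by 0% (correlation decaying with time) to about 21% (all correlations 0.85). The intermediate cases are 8–10% if it correlates 0.70–0.75 with both later scores, and 13–17% under the simulated truncation.

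At the plan's 0.85, power at 30 per arm moves from about 92% to at most 97%, so the benefit is mainly an interval up to about 11% narrower. It matters more for power if 0.85 is too high: 71% to 78% at a common 0.70.

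These figures assume a fresh PSQI at the baseline visit, a two-sided test, 0.47 in SD units and an ANCOVA of week-6 PSQI. The analysis without the screening score is not biased by leaving it out.

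**What to change.** - **D.1.3:** make the primary between-arm analysis an ANCOVA of week-6 PSQI, with baseline-visit PSQI and online screening PSQI as prespecified covariates. Prespecification matters because a covariate added after results are seen would look selective.
- **C.6 and the waitlist paragraph:** state that the baseline visit is completed before allocation is revealed, and name the PSQI as the baseline sleep measure.
- **C.5 and D.1:** use the same recall wording at screening and baseline.
- **If the screening score is itself carried forward as baseline,** say so and adjust for that single score.

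The added covariate costs one degree of freedom (57 to 56 residual at 30 per arm) and needs no new visit. The screening PSQI must be kept in the analysis file, and consent must be confirmed to cover its use.

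### The models meant to explain the sleep effect (D.1.3, D.2.2) adjust for none of the baseline depression, anxiety sensitivity, activity history or fitness data collected under C.6, so a shared baseline cause can be credited to the mediator

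*Combined protocol and SAP*

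**What the plan says.** C.6 (Baseline and Post-intervention) says: "Information about potential confounders and psychological symptoms also will be obtained using standardized methods supported by evidence of their validity". The examples it gives are "measures of symptoms of depression and anxiety, anxiety sensitivity, and physical activity history". On timing it adds: "These assessments will be repeated every 2 weeks and at the end of the six-week experiment". The same section measures VO2peak at baseline and after the intervention; its stated use is to set exercise intensity.

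The analysis text is short. For Aim 1, D.1.3 begins: "ANOVA will examine the effect of exercise training on sleep quality". It continues: "Mediation of the effect by the change in vagal tone will be tested by adding the variable as a covariate to the model", with the decision rule "A change in the significance of the f-value would indicate significant mediation". For Aim 2, D.2.2 says: "A time-varying covariate analysis will determine if sleep quality changes are explained by the change in trait anxiety or hyperarousal". This covers the assessments in weeks 2, 4 and 6.

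Neither analysis section gives a role to depression, anxiety sensitivity, physical activity history or VO2peak. Anxiety is on the C.6 list and trait anxiety does enter D.2.2, but as a candidate explanation, not as an adjustment variable. Neither section states a no-confounding assumption.

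**The concern.** Part of Aim 1 asks whether vagal tone accounts for the sleep effect, and D.1.1 hypothesises that it mediates the effect. Aim 2 asks the parallel question for trait anxiety and hyperarousal. The answers depend on the association between change in the mediator and change in sleep. Women are randomised to HIIT or waitlist, not to a change in vagal tone or symptoms, so that association is observational even within a randomised trial.

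A woman who enters with more depression or lower fitness may gain less vagal tone and also less sleep quality. A model holding only arm and mediator then attributes the shared cause to the mediator. The trial could report a mechanism that is not there while holding the data that would have guarded against it.

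**Working it through.** **1. Is the variable in a model?**

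| Collected under C.6 | D.1.3 | D.2.2 |
|---|---|---|
| Depression | no | no |
| Anxiety sensitivity | no | no |
| Physical activity history | no | no |
| Baseline VO2peak | no | no |
| Anxiety | no | trait anxiety, as the explanation under test |

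**2. The plan's own figure.** The plan gives no figure for the mediator analysis. The nearest is D.1.2: "A sample of 60 total participants will provide statistical power of 80%, at an alpha of 0.05", from an interaction effect of 0.47 and a correlation of 0.85 between repeated measurements. If 0.47 is a standardised difference, the effect in SDs of change is 0.47 / √(2 × (1 − 0.85)) = 0.47 / √0.30 = 0.858. That gives about 90% power at 30 per arm, not 80%. D.1.2 does not state the effect scale or the number of time points, so its figure cannot be verified. The present point does not depend on it.

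**3. Set-up for D.1.3.** From the documents: 30 completers per arm and alpha 0.05 (two-sided assumed). Assumed: HIIT shifts vagal change by 0.5 SD, and a baseline variable U correlates r with both changes within arm. Vagal change has no effect on sleep.

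- Mediator change = 0.5 × arm + r × U + noise
- PSQI change = −0.858 × arm − r × U + noise (lower PSQI is better)
- Within-arm variance of each change is 1

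**4. Expected bias.** With U omitted, the within-arm slope of PSQI change on mediator change is r × (−r) = −r². The spurious indirect effect is 0.5 × (−r²). At r = 0.5 it is −0.125, and 0.125 / 0.858 = 15% of the arm effect. At r = 0.3 it is −0.045, or 5%.

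**5. Simulated false-positive rates.** The change-in-F rule is read as: arm effect significant before the mediator is added and not significant after.

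| r with both changes | Mediator slope p < 0.05 | D.1.3 rule declares mediation |
|---|---|---|
| 0 | 5% | 3% |
| 0.1 | 5% | 3% |
| 0.2 | 6% | 4% |
| 0.3 | 10% | 6% |
| 0.4 | 23% | 8% |
| 0.5 | 48% | 12% |

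Repeat runs agree to about one percentage point. With U in the model and measured without error, the rates return to about 5% (slope) and 3% (rule).

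**6. Sensitivity to the assumptions.**
- With the HIIT effect on vagal change at 0.5–0.8 SD and on sleep change at 0.74–0.86 SD, the D.1.3 rule declares mediation in 6–16% of trials at r = 0.3 and 12–31% at r = 0.5, against 3–9% at r = 0.
- Two independent confounders at 0.3 / 0.4 each give slope rates of 27% / 71% and rule rates of about 8–9% / 13–15%. If the two correlate 0.6 with each other, the slope rates fall to 14% / 34%.
- If U is measured with reliability 0.8, adjustment at r = 0.5 leaves the slope rate at about 8%.

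**7. Aim 2.** These are two-point change-score calculations. D.2.2 is a time-varying analysis whose form is not specified, so no rate was computed for it.

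**The case against.** The strongest reply concerns size. D.1.3 does not decide on the mediator slope; it decides on whether the arm effect loses significance. Under that rule the inflation is modest, and at correlations of 0.2 or below it almost vanishes. The documents give no correlations, so nothing shows that the larger values apply. Confounding can also run the other way and hide mediation. All of this stands. A reader might take 48% as the rate at which this plan would falsely report mediation; the decision rule in D.1.3 does not support that.

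On Aim 2, if D.2.2 uses within-person variation, stable differences between women are already removed, and a baseline main effect adds little unless it interacts with time. That also stands, and it shapes the fix. It does not remove the risk, because baseline depression or fitness can influence how both sleep and symptoms change.

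Three broader readings are tempting and do not hold. It is not true that no analysis uses the C.6 measures: trait anxiety is in D.2.2. Not all of Aim 2 rests on the mediator–sleep link: D.2.2 also plans Hedges' d for PTSD symptoms and anxiety, which does not use it. And C.6 does not plainly label depression a confounder; it gives one list under two labels, confounders and psychological symptoms.

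**Conclusion.** The omission is clear from the text, and it exposes the explanatory conclusions of both aims. The estimate of the HIIT effect on sleep is not affected, and nothing here should be read as saying that it is biased.

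For Aim 1, under the base assumptions, a shared baseline cause correlating 0.3 to 0.5 with both changes raises the false-mediation rate of the D.1.3 rule from about 3% to 6–12%, and the false-positive rate of the mediator slope from 5% to 10–48%. These figures rest on assumed correlations, assumed HIIT effects, 30 completers per arm and a confounder that HIIT does not change. For Aim 2 the direction of the argument is the same, but no size can be claimed. The change is worth making because the data are already planned; it is not a condition for the trial's main comparison.

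**What to change.** Leave the unadjusted HIIT-versus-waitlist test as it is. In the D.1.3 model that adds change in vagal tone, and in the D.2.2 model, pre-specify one set of baseline covariates: the baseline value of the mediator under test, depression, anxiety sensitivity, physical activity history and VO2peak. If the change-in-F rule is kept, the model without the mediator that it is compared with should carry the same covariates. Otherwise a change in F could come from the covariates.

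- Use baseline values, not the two-weekly repeats, because HIIT may change the repeats.
- In a repeated-measures model, enter each covariate with its interaction with time.
- Include baseline PSQI as a covariate only if the outcome is post-baseline or change PSQI. In a repeated-measures ANOVA with baseline PSQI among the outcomes, it would stand on both sides.
- State that the mediator findings assume no unmeasured confounding.

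Cost: a few sentences of analysis text and no new data or visits. The set uses about five degrees of freedom, more with time interactions. In the two-point model, if none of the five covariates matters, power to detect a within-arm mediator–sleep correlation of 0.4 falls from about 88–89% to 86%. Measurement error in the covariates will leave some residual confounding. The weakness of the change-in-F rule itself is a separate matter that this change does not cure.
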